## LIST OF ABBREVIATIONS

MLP	magnetic levator prosthesis
IPF	Interpalpebral fissure
PI	Principal Investigator
VFQ	visual functioning questionnaire
IVI	impact of visual impairment questionnaire
MOCA	Montreal cognitive assessment
NEI	National Eye Institute
NAFL	Sodium Fluorescein
IRB	Institutional Review Board
MEEI	Massachusetts Eye and Ear Infirmary
HRPP	Human Research Protections Program
MMSE	Mini Mental Status Exam

## STATEMENT OF COMPLIANCE

The trial will be conducted in accordance with Good Clinical Practices, the U.S. Code of Federal Regulations on the Protection of Human Subjects (45 CFR Part 46), the Code of Federal Regulations applicable to clinical studies (21 CFR 312 – Investigational New Drug Application, 21 CFR 50 – Protection of Human Subjects and 21 CFR 54. The Principal Investigator at the study site Massachusetts Eye and Ear Infirmary will assure that no deviation from, or changes to the protocol will take place without prior agreement documented approval from the Institutional Review Board (IRB), except where necessary to eliminate an immediate hazard(s) to the study participants. All personnel involved in the conduct of this study have completed Human Subjects Protection Training.

## PROTOCOL SUMMARY

**Title:** Clinical Trial to improve the magnetic levator prosthesis (MLP) including the development and testing of a novel adjustable force system

**Objectives:** To improve the magnetic levator prosthesis (MLP) by development and testing of a novel adjustable force system.

**Endpoints**

1. Completion of the 2 visit protocol with acquisition of interpalpebral fissure height during resting open without the MLP, and with the MLP over 5 adjustable force levels.

Population:	Individuals with severe unilateral or bilateral ptosis (n = 19) defined as occlusion of the lower pupil margin by the lid in the resting state
Phase:	I/II
Number of Sites enrolling participants:	1
Description of Study	magnetic levator prosthesis (MLP) with compatible spectacle frames
Agent :	
Study Duration:	2 to 3 years
Participant Duration:	2 visits over 2 weeks.

\

## 1 KEY ROLES

Principal Investigator – Overall responsibility for all study related activities.

Post Doctoral Fellow- Responsible for consenting, enrolling and scheduling subjects. Also will collect, record and report all study data.

Research Technician 1 – Responsible for 3-D design and printing of prototypes.

Research Technician 2 – Responsible for producing the MLP lid magnet array. Also responsible for randomization and counterbalancing schemes.

## 2 INTRODUCTION: BACKGROUND INFORMATION AND SCIENTIFIC RATIONALE

### 2.1 BACKGROUND INFORMATION

Blepharoptosis, defined as incomplete opening of the upper eyelid, occurs due to abnormalities in the function or structure of the levator palpebrae superioris muscle, injury to or dysfunction of the superior division of the 3rd cranial nerve, or structural abnormalities.[1] Etiologies include congenital abnormalities, stroke, traumatic brain injury, tumors of the brain or face, viral illnesses, diabetes, autoimmune disorders such as myasthenia gravis, and general aging mechanisms.[1] The prevalence of blepharoptosis within the US general population is unknown; however, in Korean and U.K. general population it has been reported to be 11% [2, 3] suggesting **30 million people in the U.S.** have the disorder.

**Severe ptosis and associated ophthalmoplegia cause low vision with negative effects on function and quality of life** – Total bilateral ptosis causes profound yet potentially reversible visual impairment. Associated ophthalmoplegia results in an inability to consistently utilize the fovea, and so in many cases

magnification is useful. In bilateral 3rd nerve palsy, for example, the eye is frequently permanently abducted 30° or more, so even if the lids are opened common low vision rehabilitation interventions are needed. A similar but usually less severe situation exists in poorly controlled myasthenia gravis. When ptosis is subtotal but severe, patients are symptomatic of constricted visual field reporting problems with mobility and inability to drive. Inability to drive and effort of constant frontalis recruitment limits employability, making travel to work and sustained computer viewing very difficult. Severe unilateral ptosis (CN III palsy) causes loss of binocular peripheral field (~30°), stereopsis, and binocular summation (which is often problematic at night or other dim environments). All levels of ptosis have negative social and cosmetic impacts which are likely to affect employment and social well-being.

**Common surgical treatments** - The most common method currently used to correct ptosis involves surgical tightening of the levator muscle, or in more severe cases, frontalis sling.[1] While these procedures are a mainstay of treatment, in our experience they have disadvantages in that they do not always restore normal blink function and over-correction may result in exposure keratitis. In severe cases of ptosis a conservative approach is needed leaving the ptosis under-corrected, and so even surgical candidates may benefit from magnetic correction.

**An effective easily adjustable and/or non-surgical treatment is needed** - Substantially less attention has been given to non-surgical approaches for ptosis, which has led to lack of effective options during the early recovery period from neurological etiologies, in cases with daily variability in the ptosis such as Myasthenia Gravis, or other cases where surgery is contraindicated. Ability for the patient to easily adjust the correction as the ptosis varies would be advantageous whether it were applied surgically or not.

**Limitations of available temporary treatments** - We believe that available temporary or non-surgical treatments are ineffective and even contraindicated for many target populations. These include taping the lid(s) open and propping the lid open with a wire on the glasses (ptosis crutch).[4] Unfortunately there is a paucity of data on safety or efficacy of the ptosis crutch or taping. The crutch has to be continually adjusted to keep the lid elevated, does not allow a complete blink,[5] and poses a risk for ocular injury during adjustment or should the patient fall. We have frequently encountered use of skin tape to elevate the eye lid, but this has potentially damaging effects on the ocular surface from incomplete eye closure.

**Static magnets could provide force to elevate the eyelid while still allowing eye closure** - In most types of ptosis, while opening of the eyelid is impaired, the neuromuscular complex for eye closure (Orbicularis oculi muscle/cranial nerve (CN) VII) is intact. [1] In these cases the ptosis might be alleviated using a permanent static magnet system to provide the force to elevate the upper eyelid.[6] The static force exerted by the permanent magnet to open the eyelid should be easily overcome by the Orbicularis Oculi muscle, assuming the force of the magnet is not too great, reanimating the blink. This approach utilizes well-understood, widely available and inexpensive static magnetic materials. Electromagnets

might seem like an attractive option for the ability to modulate force; however, they generate heat and would consume too much energy to be feasible for continuous use. We had also considered electrical stimulation of the levator muscle; however, our mentors who have investigated the possibility of this approach previously indicated that repeated stimulation externally on the skin is painful in addition to difficulty accessing the levator non-surgically via this technique.

**Prior attempts to use magnets for ptosis** - The concept of correcting ptosis with magnetic force was first presented in the 1970's.[6] Conway described attaching Mu-metal 13 x 4 x 0.5 mm to the upper lid in 3 patients (attached with eyelash adhesive or blenderm tape), and a small bar magnet to the spectacles. Specifications of the ferrite spectacle magnet were not provided; however, we measured them in the photos to be ~20 x 5 x 10mm. Conway's photographs showed elevation of the eyelid when the lid and spectacle magnet were in contact; however, the ferrite magnet/Mu-metal would not have generated enough force to elevate the lid from the closed position, where there is typically 15 to 20mm separation.[5] As a result the magnet glasses would have needed frequent adjustment to bring the materials back into direct contact after each blink offering no substantial benefit over the long available ptosis crutch. It is therefore not surprising that the treatment was never commercialized. Since Conway's report, we find no publications on the use of magnets for ptosis, although they have been attempted for lagophthalmos via surgical implantation with only limited success.[7-10] Problems related to surgical implantation highlight the benefit of first refining the approach non-surgically. Static magnets are also better suited for ptosis as compared to lagophthalmos, because of the relative strength of the orbicularis compared to the levator.

## 2.2 RATIONALE

**We recently described a novel non-surgical magnetic eyewear device referred to as the Magnetic Levator Prosthesis (MLP)** that restored blinking in patients with severe paralytic ptosis.[5, 17-19] The force to lift the lid was produced by a static Neodymium magnet embedded in a glasses frame and a polymer embedded (PDMS) micro-magnet array fitted externally to the upper lid with Tegaderm IV securement film (Fig 1). The Tegaderm is FDA approved for extended wear on the skin and even as an eye covering. It generated a strong bond, keeping the magnetic array affixed to the eye lid skin for a mean of  $6 \pm 4$  days with good patient reported comfort when used for 2 hours per day during rehabilitation therapies.

**Translational Promise** – This proposed research to further improve the approach and confirm safety, feasibility, and relative efficacy for chronic management of ptosis is needed prior to commercialization. The aims of the proposed study target the clinical population of the PI who specializes in low vision rehabilitation with subspecialty in neurological visual impairments. This is a large and underserved patient population which includes many individuals with recent neurological pathology, many of whom

are residing in inpatient rehabilitation facilities (IRF). IRFs provide 24 hour medical supervision and rehabilitation therapies to patients who are medically stable and are able to participate in a minimum of 3 hours/day of therapy. There are 1,165 IRFs in the U.S.[20] with an average length of stay of 16 days.[21] If we conservatively estimate an average of 50 beds per 1,165 IRFs revolving every 16 days there should be approximately 1.2 million admissions and discharges per year in IRFs nationwide. Of that population, ~32% are recovering from stroke and 6% from traumatic brain injury.[21] Prevalence of CN III palsy in stroke populations has been reported at 2.5%,[22] and 4.4% in TBI (internal data). Therefore, the estimated national target population for temporary management of severe ptosis in IRFs alone is 12,000 patients annually. In our IRF, internal review found a rate of 24 cases of severe ptosis in 2015-2016. No one stands to directly and immediately benefit more from this technology than patients with severe bilateral ptosis. While this is presumed to be a rare situation we have encountered 8 such patients in the past 2 years without any active recruiting effort. We have also encountered multiple patients with severe unilateral ptosis obscuring the vision in their better eye for whom surgery was contraindicated. There is no available option for these patients other than taping the lids open or the ptosis crutch with the aforementioned problems with these approaches.

**Scientific Premise:** In summary, premise for the proposed work is that ptosis is a major public health concern which to this point has received less attention than its lagophthalmos counterpart despite the fact that it causes similar discomfort and disability (but without the extreme consequence of exposure and scarring). Better non-surgical options are needed. Weaknesses in prior work in the field concerning magnetic correction included use of ferrite magnets, inadequate adhesion methods for external placement, moving too soon to surgical implantation, and lack of evidence from randomized controlled trials to guide clinical approaches. We will fill a significant gap in the field in terms of non-surgical correction while not excluding use of data and methodology to advance success with surgical implantation.

IT IS ALSO POSSIBLE THAT A REDUCED BLINK REFLEX COULD ELEVATE THE RISK OF FOREIGN BODY IN THE CASE OF PROJECTILES. ALL PARTICIPANTS WILL BE FITTED WITH SAFETY GRADE OR POLYCARBONATE LENSES, IN THEIR PRESCRIPTION (OR NON-PRESCRIPTION PLANO IF THEY REQUIRE NONE). PARTICIPANTS WILL BE INSTRUCTED TO WEAR ADDITIONAL PROTECTIVE EYEWEAR AND TO AVOID PLACES LIKE MACHINE SHOPS WHERE THERE COULD BE METAL SHAVINGS. THE LID MAGNETS ARE NOT STRONG ENOUGH TO PROPEL A MAGNETIC/METAL OBJECT TOWARDS THE EYE AND THE MAGNETS SHOULD ACTUALLY REDUCE THE RISK FOR METALLIC FOREIGN BODY PROJECTILE ENTERING THE EYE BY REDIRECTING IT TOWARDS THE SPECTACLE MAGNET; HOWEVER, THERE IS RISK THAT METAL SHAVINGS COULD ACCUMULATE AROUND THE MAGNETS IF THE DEVICE IS USED IN A SITUATION SUCH AS A WORKSHOP WHERE SHAVINGS ARE PRESENT. WHILE THESE WOULD NOT BE PROJECTED INTO THE EYE, MINOR INJURY MAY RESULT IF THE SHAVINGS GET AROUND THE EYE AND THEN ARE RUBBED INTO OR SPRINKLE INTO THE EYE(S). STANDARD SAFETY GOGGLES WILL FIT OVER THE SPECTACLES AND PARTICIPANTS WILL BE INFORMED THAT THEY SHOULD BE WORN AS THEY NORMALLY WOULD.

2.3.2  
KNOWN POTENTIAL BENEFITS

Possible treatment for restoration of eyelid motility in subjects who wear the device comfortably.

### 3 OBJECTIVES AND PURPOSE

To improve the magnetic levator prosthesis (MLP) by development and testing of a novel adjustable force system. If endpoints are met and the device is determined to be feasible the study will continue to a randomized clinical trial comparing the MLP against the predicate treatment of taping the lids (future IRB application).

### 4 STUDY DESIGN AND ENDPOINTS

#### 4.1 DESCRIPTION OF THE STUDY DESIGN

A blinded study to perform measurements and experiments to improve the magnetic levator prosthesis (MLP) including the development and testing of a novel adjustable force system.

##### 4.2.1 PRIMARY ENDPOINTS

Completion of the 2 visit protocol with acquisition of interpalpebral fissure height during resting open without the MLP, and with the MLP over 5 adjustable force levels.

### 5 STUDY ENROLLMENT AND WITHDRAWAL

#### 5.1 PARTICIPANT INCLUSION CRITERIA

1. Presence of Blepharoptosis for at least one eye which occludes the visual axis in the resting state (no frontalis drive), 2. Moderate cognitive function or better defined as greater than or equal to 18 out of 30 on a pre-screening of the Mini-Mental State Exam. 3. Age 5 or older.

#### 5.2 PARTICIPANT EXCLUSION CRITERIA

1. Absence of ptosis which occludes the visual axis or presence of a corneal ulcer of any size. 2. Age less than 5, Severe Cognitive impairment defined as MMSE score <18, behaviors consistent with delirium (combinations of disorientation, hallucinations, delusions, and incoherent speech), or lethargy.

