## 7 STUDY PROCEDURES AND SCHEDULE

### 7.1 STUDY PROCEDURES/EVALUATIONS

#### 7.1.1 STUDY SPECIFIC PROCEDURES

A cognitive pre-screening to guide the consent process will be administered as described in section 13.3.2. After consent, participants will have their acuity measured (refraction as needed), slit lamp with Nafl & NEI scale. Next, the MLP will be placed on the patient and video recordings made for 1 minute (comfort monitored with a 10-point scale during this period). Next, the effect of force adjustment via magnet rotation on lid position will be measured. The spectacle magnet will be rotated (settings labeled 1-4, counterbalanced), and videos recorded for another minute at each rotational increment. For video recording we will have 2 cameras: 1 straight on and the other angled up (to capture upper lid apposition to globe, Fig 5d&e). Recording will be done with a blue filter and NaFl to simultaneously document tear film. Additional NaFl will be added over the trial at the clinical staff discretion as needed. Once optimal rotational increment is found, a 20 minute trial at that setting will be performed with repeat of video recording with comfort and efficacy scale. Afterwards, the array will be removed and an array with the alternative polarization will be applied. We will then record for 1 min getting comfort and efficacy data and repeating the rotation experiment followed by another 20-minute trial. At the end of the study visit we will repeat visual acuity, slit lamp with Nafl & NEI cornea scale, and video recordings with comfort scale will be repeated. As this is a fitting and optimization process, it is possible that additional visits will be necessary in order to make modifications, but these will be optional.

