### 7.3 STUDY SCHEDULE

#### 7.3.1 SCREENING

**Pre-Screening:** In order to guide the consent/assent process, the approved study staff will administer a pre-consent cognitive screening using the Mini-Mental State Exam (MMSE). If score is 18-23 (maximum of 30) representing mild cognitive impairment (Tombaugh et al 1992), candidates will be asked return with a caregiver (if one is not present). If score is <18, they will not be eligible. **Screening/Study Intake:** Participants will have their acuity measured (refraction as needed), slit lamp with Nafl & NEI scale.

**Inclusion Criteria:** Presence of Blepharoptosis for at least one eye which occludes the visual axis in the resting state (no frontalis drive), moderate cognitive function or better defined as greater than or equal to 18 out of 30 on a pre-screening of the Mini-Mental State Exam, age 5 or older. **Exclusion Criteria:** Absence of ptosis which occludes the visual axis or presence of a corneal ulcer of any size. Age less than 5, Severe Cognitive impairment defined as MMSE score <18, behaviors consistent with delirium (combinations of disorientation, hallucinations, delusions, and incoherent speech), or lethargy. These individuals must be excluded since participation requires competent self-care, reliable responses and

cooperation during fitting of the device. Children need to be included because they represent an important target population (pediatric neuro-muscular conditions), and because facial structure and skin characteristics may result in a different response than adults

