#### 7.3.7 SCHEDULE OF EVENTS TABLE

Procedures	VISIT 1 (ASSESSMENTS WILL BE REPEATED IF PARTICIPANT AGREES )	Visit 2 (1 week +/-2 days Visit 1 assessments will be repeated if participant agrees and the clinical staff will determine if this is clinically appropriate
Follow Up Phone Call		X
Visual Acuity (refraction if needed)	X	X
Slit Lamp Exam	X	X
NEI corneal staining scale	X	X
Baseline Video Recording	X	X
Eye Lid Prep	X	

Procedures	VISIT 1 (ASSESSMENTS WILL BE REPEATED IF PARTICIPANT AGREES)	Visit 2 (1 week +/- 2 days Visit 1 assessments will be repeated if participant agrees and the clinical staff will determine if this is clinically appropriate
Measurement of force to open the ptotic lid	X	
Polarity experiment, case 1 (apply lid magnet array)	X	
Video recording	X	X
10 point comfort and efficacy scale	X	X
spectacle magnet rotation experiment	X	
20 minute trial at optimum rotation	X	
Repeat Video Recording	X	
Repeat 10 point comfort and efficacy scale	X	
Polarity experiment, case 2 (apply lid magnet array)	X	
spectacle magnet rotation experiment	X	
20 minute trial at optimum rotation	X	
Video recording	X	
10 Point Comfort and Efficacy Scale		X
Repeat visual acuity	X	
Repeat Slit Lamp Exam	X	
Repeat NEI Nafl scale	X	
Clinical Decision		X

<Insert text>

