## 7.5 CONCOMITANT MEDICATIONS, TREATMENTS, AND PROCEDURES

Oral and ophthalmic concomitant medications will be reviewed and recorded to confirm the patient does not have any systemic disease that would interfere with the study assessments and or data.

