## 7.6 PROHIBITED MEDICATIONS, TREATMENTS, AND PROCEDURES

Ophthalmic ointment or skin ointment applied near the eyes interferes with adhesion of the lid magnet and will need to be discontinued at least 1 day prior to the study. Patients may continue with artificial tears.

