# 8 ASSESSMENT OF SAFETY

## 8.1 SPECIFICATION OF SAFETY PARAMETERS

The safety of the study device will be evaluated at every visit following the enrollment visit and will be defined by the incidence of related adverse events. Specifically, we will evaluate:

- **Systemic safety:** Incidence and severity of systemic adverse events during the study (adverse events spontaneously reported or observed by the Research Assistant).
- **Ocular safety:** Incidence and severity of ocular adverse events during the study (ophthalmic examination, adverse events spontaneously reported).
- **SAFETY CUTOFFS: Should visual acuity decrease more than 2 lines, worsening of corneal rating of more than 1.5 points or other ocular surface ratings more than 2 points, and comfort rating lower than 5/10; study activities will cease for at least 1 week and an adverse event report to the IRB. Serious adverse events which will result in immediate dismissal from the study (and treatment) include: 1) development of a corneal epithelial defect or infiltrate without epithelial defect or 2) broken skin on the eyelid.**

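### The entry criteria exclude a corneal ulcer but not an epithelial defect, infiltrate or broken lid skin, the findings that bring immediate dismissal once on study

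*Combined protocol and SAP*

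**What the plan says.** Section 5.2 of the combined protocol and SAP lists the exclusions. The one that concerns the eye reads "Absence of ptosis which occludes the visual axis or presence of a corneal ulcer of any size". The remaining items cover age, cognition, delirium and lethargy. Section 7.3.1 restates the same list. The inclusion criteria in 5.1 require ptosis over the visual axis, an adequate MMSE score and age 5 or older; they do not ask for an intact cornea or intact lid skin.

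The intake examination in 7.3.1 is described as follows: "Participants will have their acuity measured (refraction as needed), slit lamp with Nafl & NEI scale". Section 7.1.1 puts the same examination after consent and then continues: "Next, the MLP will be placed on the patient and video recordings made for 1 minute". After the first round of rotation settings and a 20-minute trial, it says: "Afterwards, the array will be removed and an array with the alternative polarization will be applied". Section 6.1 explains that each array is held on the upper lid by an adhesive securement film.

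Section 8.1 names the events that end participation and treatment immediately: "1) development of a corneal epithelial defect or infiltrate without epithelial defect or 2) broken skin on the eyelid". It lists them as serious adverse events.

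**The concern.** The protocol treats three findings as serious enough to stop the device at once, yet does not say that a person who arrives with one of them should not be fitted. The intake slit lamp would be the natural place to stop, but no finding or score from it is linked to eligibility.

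What is at stake is participant protection. Adhesive film would be applied to a lid whose skin may be broken, or a lid-elevating force to an eye whose epithelium may be open or infiltrated. The film would then be peeled off and applied again. The protocol gives some reason to think that candidates could arrive with such findings: section 2.1 says that the team often meets patients who tape their lids, with possible damage to the ocular surface, and that the ptosis crutch carries a risk of ocular injury. Children from age 5 and adults with MMSE scores of 18 to 23 are eligible, so a written rule is safer than reliance on reported symptoms.

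**Working it through.** The plan states no figure on this point. The check sets the entry list beside the on-study list and then asks whether any other section closes the gap.

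**Step 1: the two lists.**

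| Finding | Excluded at entry (5.2, 7.3.1)? | Immediate dismissal on study (8.1)? |
|---|---|---|
| Corneal ulcer | Yes, any size | Not named separately |
| Corneal epithelial defect, not an ulcer | No | Yes |
| Infiltrate without epithelial defect, not an ulcer | No | Yes |
| Broken lid skin | No | Yes |

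Of the 3 findings named for dismissal, 0 are named at entry. A corneal case that amounts to an ulcer is already excluded, so the gap concerns the remainder and all cases of broken lid skin.

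**Step 2: do the 8.1 rules act at intake?** Section 8.1 says that device safety is evaluated at each visit after enrollment. Its corneal cutoff is a worsening of more than 1.5 points, and its first dismissal item is about a defect or infiltrate that develops. Neither acts on a corneal finding already present at baseline. The second item, broken lid skin, lacks the word for development, but it stands under serious adverse events. The natural reading is an event that arises on study.

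**Step 3: other sections.**
- 7.1.1 and 7.3.1: the slit lamp with fluorescein is done, with no eligibility consequence.
- 7.3.7: "Baseline Video Recording" is listed before the lid preparation, again with no stop attached.
- 7.5: medications are reviewed "to confirm the patient does not have any systemic disease that would interfere with the study assessments"; this is not a check of cornea or lid skin.
- 10.4.4: magnified images of the ocular surface and lid skin are planned, with no stated timing relative to fitting and no eligibility consequence.
- 5.4.1: the investigator may withdraw a subject for safety or best interest; this is discretion, not a criterion.

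**Step 4: scheduled exposure at Visit 1, from 7.1.1.** Per array: 1 minute of initial recording + 4 labelled settings × 1 minute + a 20-minute trial = 25 minutes. Two arrays: 2 × 25 = 50 minutes, with 2 applications and at least 1 removal between them. Fitting time, the end-of-visit recordings and any optional repeat at Visit 2 are not counted.

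**The case against.** The strongest reply is that stops already exist in practice. The slit lamp follows consent and precedes the first array, so a person with a visible defect is by then a subject who can be withdrawn under 5.4.1 before anything is applied. Section 10.4.4 adds imaging of surface and skin, and examiners experienced with the eye. Broken lid skin in 8.1 could also be read to cover a lesion present at intake. Most examiners would probably defer such a candidate unprompted. All of this lowers the risk. It does not close the gap, because the withdrawal is discretionary, the images have no stated timing or consequence, and the reading of 8.1 is not the natural one.

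A second reply is that an entry list and a stopping list serve different purposes, so counting 3 against 0 proves little. That is fair as far as it goes. A reader might infer that the protocol contradicts itself, and it does not: 8.1 deals with events on study, and 5.2 with selection. The point is only that the written rule admits someone whom the protocol would stop at once if the same finding arose later.

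The frequency may also be low. Section 2.2 describes ptosis as free of the extreme consequences of exposure and scarring, and section 13.2 calls the protocol minimal risk. Nothing in the documents gives the rate at intake.

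Finally, a reader might infer from 7.6 ("Ophthalmic ointment or skin ointment applied near the eyes interferes with adhesion of the lid magnet and will need to be discontinued") that a candidate under treatment for such a lesion would be made to stop it. The documents do not say what the ointment is for, and it may be simple lubrication. The point does not rest on it.

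**Conclusion.** The gap is real and modest. On the written criteria, a candidate with a non-ulcer corneal epithelial defect, a corneal infiltrate or broken skin on the lid to be fitted may enter and have two adhesive arrays applied in sequence, for about 50 scheduled minutes at Visit 1. This rests on two readings: that the 8.1 dismissal items refer to events arising on study, and that withdrawal under 5.4.1 is not an entry rule.

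The number of people affected cannot be estimated from the documents. A reader might also infer that such candidates would bias the interpalpebral fissure results; nothing in the documents shows such an effect. The point is one of participant safety and consistent practice, and a low-cost improvement rather than a flaw that invalidates the design.

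**What to change.** 1. Add to the exclusions in 5.2 and 7.3.1: *corneal epithelial defect, corneal infiltrate, or broken skin on the eyelid to be fitted; may be re-screened once healed*.
2. At the intake examination already scheduled, and before the lid preparation, record each of the three as present or absent, with the lid skin included.
3. Recheck the skin of the fitted lid after the first array is removed and before the second is applied.

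Leave 8.1 as it stands. Narrowing its second item to newly developed lesions would remove the only wording that might cover broken skin present at intake.

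The cost is one sentence in two sections and a few tick boxes on the Visit 1 data sheet; no extra visit is needed. The downside is that a few candidates would be deferred until healed or excluded, which could slow recruitment slightly in a study of 19.
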